6. VERSION HISTORY

| Version | Date | Author | Description of main modifications – amendments |
|---------|----------------|------------|--|
| 1.0 | 17 June 2022 | ██████████ | Initial version of the Clinical Investigation Plan |
| 2.0 | 11 August 2022 | ██████████ | Update of the Clinical Investigation Plan to address Ethics Committee's comments: 
 • Description of patient's usual care pathway and link with investigation information and inclusion process (section 9.5.3.1) • Addition of a pregnancy test for women of childbearing potential (sections 8, 9.5.5.1 and 9.5.5.5). |

| | | |
|--------|---|---|
| RGnCON | Clinical Investigation Plan Version 2.0 - 11 August 2022 |  |
|--------|---|---|

7. ABBREVIATIONS

| Abbreviation | Description |
|--------------|---|
| AD | Alzheimer's Disease |
| ADAS-Cog | Alzheimer's Disease Assessment Scale-cognitive subscale |
| ADE | Adverse Device Effect |
| AE | Adverse Event |
| ANSM | Agence Nationale de Sécurité des Médicaments et produits de santé - French National Agency for the Safety of Medicines and health products |
| ATC | Anatomical Therapeutic Chemical |
| ASADE | Anticipated Serious Adverse Device Effect |
| BD | Base Down |
| BI | Base In |
| BO | Base Out |
| BU | Base Up |
| CIP | Clinical Investigation Plan |
| CNIL | Commission Nationale de l'Informatique et des Libertés - French National Commission on Informatics and Freedoms |
| DD | Device Deficiency |
| eCRF | electronic Case Report Form |
| FAS | Full Analysis Set |
| GCP | Good Clinical Practice |
| GDPR | General Data Protection Regulation |
| GFAP | Glial Fibrillary Acidic Protein |
| HIA3 | Head Injury Assessment - Form 3 |
| IEC | International Electrotechnical Commission |
| IFU | Instruction For Use |
| IL | InterLeukin |
| ISO | International Organization for Standardization |
| IWRS | Interactive Web Response System |
| LED | Light Emitting Diode |
| LH | Left Hyperphoria |
| MedDRA | Medical Dictionary for Regulatory Activities |
| NA | Not Applicable |

| | | |
|--------|---|---|
| RGnCON | Clinical Investigation Plan Version 2.0 - 11 August 2022 |  |
|--------|---|---|

| Abbreviation | Description |
|--------------|--|
| NPC | Near Point of Convergence |
| PBM | PhotoBioModulation |
| PT | Preferred term |
| Rh | Right hypophoria |
| RH | Right Hyperphoria |
| SADE | Serious Adverse Device Effect |
| SAE | Serious Adverse Event |
| SCAT5 | Sport Concussion Assessment Tool - 5 th edition |
| SMS | Static Magnetic Stimulation |
| SOC | System Organ Classes |
| TBI | Traumatic Brain Injury |
| TMT A&B | Trail Making Test part A and B |
| UCH-L1 | Ubiquitin C-terminal Hydrolase-L1 |
| USADE | Unanticipated Serious Adverse Device Effect |
| WHO | World Health Organization |

8. SYNOPSIS

| | |
|---------------------------------------|---|
| Title | Pilot clinical investigation evaluating the safety and performance of RGn550 in treating sportspeople suffering from acute concussion syndrome (RGnCON) |
| ID-RCB Number | 2022-A01319-34 |
| Investigational Medical Device | 
RGn550 is a reusable non-invasive class IIa electromedical device that is manufactured by REGEnLIFE and not CE-marked yet.
 
The device combines two technologies:
 
• PhotoBioModulation (PBM), which involves exposure to directional low-power and high-fluence monochromatic or quasi-monochromatic light from the red to near-infrared wavelengths ($\lambda = 600-1,100$ nm) using lasers and Light Emitting Diodes (LEDs)• Static Magnetic Stimulation (SMS), which consists in the application of a static magnetic field using a neodymium magnet. 
[REDACTED]
 
[REDACTED]
 
[REDACTED]
 
[REDACTED]
 
[REDACTED]
 
The device is intended, on medical opinion, to treat acute concussion syndrome (inferior or equal to 72h). It is intended for use by physicians and nurses trained in the use of RGn550 on adult patients. The treatment area is the head.
 |
| Investigation Rationale | 
Considering:
 
• The promising results of transcranial PBM in concussion that were published in the literature,• The effect of a previous version of the device on neuroinflammation demonstrated pre-clinically and the fact that a neuroinflammatory response is involved in concussion's physiopathology,• The good safety results obtained in Alzheimer's Disease (AD) patients in the pilot clinical investigation on a previous version of the device, REGEnLIFE wishes to conduct a pilot clinical investigation on RGn550 to evaluate its safety and explore its performance in treating patients with acute concussion syndrome. |
| Overall Design | 
RGnCON is a prospective, comparative, randomized, simple-blinded, monocentric, pilot clinical investigation.
 
It involves two parallel groups differing in terms of treatment frequency: half of the patients will be treated with 5 Hz, the other half with 10 Hz.
 |
| Objectives | 
Primary objective:
 
• To evaluate the incidence of RGn550's Adverse Device Effects (ADEs) in acute concussion syndrome, when used to deliver, either at a frequency |

| | | |
|---------------------------------|---|--|
| | 
of 5 or 10 Hz, two 20-min treatment sessions at 1 week apart.
 
Secondary objectives:
 
• To evaluate the incidence of RGn550's ADEs per severity, Adverse Events (AEs) and Device Deficiencies (DDs)• To evaluate the effect of RGn550, after the first and second treatment sessions and then 45 days after the second treatment session, on:
◦ Automated oculomotor and oculopostural functions◦ Balance function◦ Executive function• To assess the effect of RGn550 on concussion syndrome symptoms 7 days after the first treatment session as well as 7 and 45 days after the second treatment session• To evaluate the effect of RGn550 on blood markers that are involved in the pathogenesis of concussion 45 days after the second treatment session. | |
| Investigation Population | 
Adult sportspeople with acute concussion syndrome resulting from sport practice who can participate in a clinical investigation per the law and are able to meet treatment sessions and complete requested assessments will be included.
 
Inclusion criteria:
 
• Male or female aged at least 18 years old• Suffering from concussion syndrome resulting from a shock that occurred during sport practice less than 72h ago, as confirmed by neurological examination via the Head Injury Assessment - Form 3 (HIA3) tool• Affiliated to French social security• Who provided a dated and signed informed consent form. 
Non-inclusion criteria:
 
• Patient protected by a French legal measure ("sauvegarde de justice", "tutelle" or "curatelle")• Patient not able to express his/her consent• Patient deprived of liberty or hospitalized without consent• Woman who is pregnant or breastfeeding, or who plans to become pregnant or breastfeeding during the investigation, or who has the capacity to conceive but is not using a reliable contraceptive method as deemed by the investigator• Patient living in a medical facility• Patient who experienced a surgery at the treatment application area (head) within 3 months prior to inclusion• Patient with skin lesions on the treatment application area (head)• Patient with a short-term life-threatening pathology (e.g., evolving cancer; non-stable heart failure; severe hepatic, renal or respiratory failure, etc.)• Patient diagnosed with a heart attack within 3 months prior to inclusion• Patient implanted with ferromagnetic material• Patient implanted with a pacemaker• Patient with a risk of epileptic seizure or other non-degenerative central | |

| | | |
|------------------------------|--|--|
| | 
nervous system diseases
 
• Patient with major physical or neurosensorial disorders that may interfere with assessments• Patient with chronic psychosis or psychotic episodes• Patient addicted to alcohol or drugs• Patient treated with antidepressant or benzodiazepine• Patient who participated to another investigation/study involving the use of an investigational medical device/drug within the 30 days prior inclusion• Patient not able to meet treatment sessions as deemed by the investigator• Patient not able to complete requested investigation assessments as deemed by the investigator. | |
| Investigation Conduct | 
Three onsite visits will be performed at the following timepoints:
 
• Day 0 (D0): Inclusion, randomization (to the 5 Hz or 10Hz treatment group) and first treatment session• Day 7 (D7): Second treatment session• Day 52 (D52): Evaluation 45 days after the last treatment session. 
In addition, at Day 14 (D14), the patient will be asked to remotely assess his/her concussion syndrome symptoms.
 
The overall investigation duration, which corresponds to the inclusion period and the follow-up period, will be of 6 months approximately (4 months of inclusion and 52 days of follow-up).
 | |
| Endpoints | 
Primary endpoint:
 
• Incidence of RGn550's ADEs throughout the investigation 
Secondary endpoints:
 
• Incidence of RGn550's ADEs per severity (mild, moderate and severe) throughout the investigation• Incidence of RGn550's AEs throughout the investigation• Incidence of RGn550's DDs throughout the investigation• Evolution, before and after treatment session at D0 and D7 and then at D52, of:
○ Automated oculomotor and oculopostural functions, as assessed through:
▪ Convergence, evaluated with the measure of the Near Point of Convergence (NPC)▪ Deviations, evaluated with the cover test and Maddox rod test○ Balance function, as assessed through the following static stabilometric parameters:
▪ Statokinesigram area▪ Left/right distribution• Evolution, before treatment session at D0 and after treatment session at D7 of executive function, as assessed with the Trail Making Test part A and B (TMT A&B)• Evolution of concussion syndrome symptoms as assessed by the patient | |

| | | |
|----------------------------------|--|--|
| | 
with the Sport Concussion Assessment Tool – 5th edition (SCAT5) symptom evaluation tool at D0 before treatment, D7 before treatment, D14 and D52
 
Evolution from D0 before treatment to D52 of the concentration of the following blood markers:
Anti-inflammatory cytokines InterLeukin (IL)-1 receptor antagonist, IL-4, IL-6, IL-10, IL-11 and IL-13S100 calcium binding protein B (S100B)Glial Fibrillary Acidic Protein (GFAP)Ubiquitin C-terminal Hydrolase-L1 (UCH-L1). | |
| Sample Size Justification | It is planned to include 50 patients in this investigation. For such a sample size, the probability of observing at least one ADE will be 0.87 considering a probability of ADE of 0.04. | |
| | 
All analyses will be performed in the Full Analysis Set (FAS), which will comprise all included patients who have been treated at least once with RGn550 device. Patients will be assigned to the treatment group as treated.
 
The global significance level (type I error rate) will be set at $\alpha = 0.05$ (two-sided). Adjustment for multiplicity is not applicable for the primary endpoint and no adjustment for multiplicity is planned for secondary endpoints.
 | |
| Statistical Analysis | 
Primary endpoint analysis
 
The proportion of subjects with at least one ADE will be calculated along with the 95% exact Clopper-Pearson confidence interval in the FAS, by treatment groups and overall.
 
Secondary endpoints analysis
 
For ADEs per severity, a descriptive analysis with 95% exact Clopper-Pearson confidence interval of mild, moderate and severe ADEs will be provided in the FAS, by treatment groups and overall.
 
All AEs will be described in the FAS, for each System Organ Class (SOC) and Preferred Term (PT) class using MedDRA (Medical Dictionary for Regulatory Activities) terminology, by treatment groups and overall.
 
All DDs will be described in the FAS, by treatment groups and overall.
 
The secondary performance analyses will be performed in the FAS by treatment groups, excluding data that would be collected after the following intercurrent event: treatment group switch during follow-up.
 
Imputation of missing data will be handled by the mixed model (details will be provided in the Statistical Analysis Plan).
 
A sensitivity analysis will be conducted on the secondary performance endpoints in the FAS without excluding any data collected after intercurrent events.
 | |
| Provisional timelines | 
Regulatory submission: June 2022Site initiation: August-September 2022Patient recruitment: September 2022 (first patient first visit) - December 2022 (last patient first visit)Last visit last patient: February 2023Database lock: March-April 2023 | |

- Statistical analysis and clinical investigation report: May-July 2023

| | | |
|--------|---|---|
| RGnCON | Clinical Investigation Plan Version 2.0 - 11 August 2022 |  |
|--------|---|---|

| | D0 | | D7 | | D14 (remote) | D52 |
|--|------------------|-----------------|------------------|-----------------|-----------------|-----|
| | Before treatment | After treatment | Before treatment | After treatment | | |
| Patient information / Informed consent | X | | | | | |
| Eligibility criteria | X | | | | | |
| Pregnancy test for women of childbearing potential | X | | | | | |
| Randomization | X | | | | | |
| Demographic and clinical data | X | | | | | |
| NPC | X | X | X | X | | X |
| Cover test | X | X | X | X | | X |
| Maddox rod test | X | X | X | X | | X |
| Stabilometric test | X | X | X | X | | X |
| TMT A&B | X | | | X | | |
| SCAT5 symptom evaluation tool | X | | X | | X | X |
| Blood sampling | X | | | | | X |
| 20-min treatment session | X | | X | | | |
| Collection of AEs and DDs that previously occurred | | X | X | X | | X |

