9.6. Statistical Considerations

9.6.1. Sample Size Justification

For a sample size of 50 patients, the probability of observing at least one ADE will be 0.87 considering a probability of ADE of 0.04. The sample size calculation was performed with SAS® v9.4.

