9.6.2. Analysis Population

All analyses will be performed in the **Full Analysis Set (FAS)**, which will comprise all included patients who have been treated at least once with RGn550 device. Patients will be assigned to the treatment group as treated.

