9.13.1.6. Device Deficiency (DD)

Any inadequacy in the identity, quality, durability, reliability, safety or performance of an investigational device, including malfunction, use errors or inadequacy in information supplied by the manufacturer (*Regulation 2017/745*).

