9.13.3. Safety Reporting to Sponsor

Per Article 80 of the European Regulation 2017/745, the following events shall be recorded:

- Any AE of a type identified in the CIP as being critical to the evaluation of the results of that clinical investigation
- Any SAEs
- Any DD that might have led to a SAE if appropriate action had not been taken intervention had not occurred, or circumstances had been less fortunate
- Any new findings in relation to the above events.

The following events that occur in patients included in RGnCON from inclusion to the end of the 52-day follow-up period will thus be recorded:

- All AEs, including SAEs
- All DDs
- Any new findings in relation to AEs and DDs.

AEs will be reported using the Adverse Event form of the eCRF while DDs will be reported using the Device Deficiency form. The date of the event, its severity, causality, treatment and resolution will notably be collected.

These events will be reported immediately to REGEnLIFE and no later than 3 calendar days after the investigator becomes aware of the event.

If needed, the investigations site team or [REDACTED] can contact REGEnLIFE's materiovigilance department via email ([contact]) or phone ([contact]).

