### 6.2. Secondary endpoints

#### 6.2.1. Secondary safety endpoints

The following secondary safety endpoints will be computed using data recorded in the “Adverse Event (AE)” Form:

- Proportion of patients with at least one mild ADE
- Proportion of patients with at least one moderate ADE
- Proportion of patients with at least one severe ADE
- Proportion of patients with at least one adverse event (AE)
- Proportion of patients with at least one device deficiencies (DDs)

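### A device deficiency that prevents every treatment session would be recorded but left out of the device deficiency incidence, because the protocol describes deficiencies only in treated patients

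*Protocol*

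**What the plan says.** **Endpoint.** Protocol 9.5.4.2 makes DD incidence over the whole investigation a secondary endpoint. SAP 6.2.1 turns it into the proportion of patients with one or more DDs.

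**Analysis set.** The synopsis and protocol 9.6.3.2 both state: "All DDs will be described in the FAS, by treatment groups and overall". Protocol 9.6.2 defines the FAS as the set "which will comprise all included patients who have been treated at least once with RGn550 device", and adds: "Patients will be assigned to the treatment group as treated". SAP section 5 keeps the requirement of at least one treatment. SAP 8.4.2, which holds the DD row, names no population. SAP section 10 declares no change on this point.

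**Recording.** Protocol 9.13.3 opens its recording rule with "The following events that occur in patients included in RGnCON from inclusion to the end of the 52-day follow-up period" and then lists all DDs. Protocol 9.13.1.6 defines a DD broadly, "including malfunction, use errors or inadequacy in information supplied by the manufacturer". Nothing in that definition requires a session to have been delivered.

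**Sequence.** Under protocol 9.5.5.1, inclusion and randomisation come before the first session, at the same D0 visit. Under 9.5.1, a second device of the same frequency may be used if the first malfunctions.

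**The concern.** Recording starts at inclusion, but the summary starts at first treatment. Between the two, a patient can be included, randomised and affected by a deficiency, and then never be treated. The event being counted is then what removes the patient from the count.

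Restricting adverse device effects (ADEs) to treated patients is sensible, because an ADE is by definition an adverse event related to use of the device. The same argument does not carry over to DDs, where failure to deliver treatment can itself be the outcome. If the backup device solves the problem, the patient is treated, enters the FAS and the DD counts. If it does not, the DD drops out. The omission therefore falls on the deficiencies with the greatest consequence for delivery, in a study of a device that is not yet CE-marked.

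**Working it through.** **1. The plan's own figure.** Protocol 9.6.1 states that "the probability of observing at least one ADE will be 0.87 considering a probability of ADE of 0.04". With N = 50: 1 − 0.96^50 = 0.8701. The figure reproduces. It concerns ADEs and is unaffected by how DDs are summarised. The documents give no planning figure for DDs.

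**2. Can an included patient with a DD fall outside the FAS?**
- Recording window: from inclusion (protocol 9.13.3).
- Event definition: no delivered session needed (protocol 9.13.1.6).
- Summary: FAS only (synopsis; protocol 9.6.3.2).
- FAS entry: at least one treatment (protocol 9.6.2; SAP section 5).

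Yes. No other planned DD summary covers such a patient.

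**3. Direction.** Let n be the number included, k the patients never treated because of a DD, and x the treated patients with a DD. Assume nobody is untreated for another reason.

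- Plan: x/(n − k)
- All included: (x + k)/n
- Difference: (x + k)/n − x/(n − k) = (k/n) × [1 − x/(n − k)]

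This is never negative, so leaving these patients out cannot raise the reported rate.

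**4. Size.** n = 50 comes from the synopsis: "It is planned to include 50 patients in this investigation". The documents give no value for k, so k and x are assumptions. Intervals are 95% Clopper-Pearson, the method the protocol names for its safety proportions.

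| k | x | Plan (FAS) | All included |
|---|---|---|---|
| 0 | 0 | 0/50 = 0% (0 to 7.11) | 0/50 = 0% (0 to 7.11) |
| 1 | 0 | 0/49 = 0% (0 to 7.25) | 1/50 = 2.0% (0.05 to 10.65) |
| 1 | 1 | 1/49 = 2.04% (0.05 to 10.85) | 2/50 = 4.0% (0.49 to 13.71) |
| 2 | 0 | 0/48 = 0% (0 to 7.40) | 2/50 = 4.0% (0.49 to 13.71) |
| 3 | 0 | 0/47 = 0% (0 to 7.55) | 3/50 = 6.0% (1.25 to 16.55) |

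Check with k = 1, x = 1: (1/50) × (1 − 1/49) = 1.96 percentage points, and 4.00 − 2.04 = 1.96.

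By arm, assuming 25 per arm from the 1:1 allocation, k = 1 and no other DD: 0/24 = 0% (0 to 14.25) against 1/25 = 4.0% (0.10 to 20.35).

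**The case against.** **The trigger is narrow.** The deficiency must arise before any exposure at D0, the backup device must fail to resolve it, and no session may ever follow. No minimum duration is set for being treated, so a session that starts and then fails may keep the patient in the FAS with the DD counted. All of this stands, and it is why the point is minor. Much of the device description is missing from the public text, so the likelihood of a deficiency common to both devices cannot be judged.

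**No safety information is lost.** Under protocol 9.13.3 every DD goes to the sponsor within 3 calendar days, and under SAP section 9 all eCRF data are listed. This also stands. A listing is still not the incidence that the endpoint promises.

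**SAP 8.4.2 may already be wide enough.** It names no population and says that every AE collected in the eCRF is used. That sentence concerns AEs. For DDs the protocol's FAS rule remains the only one stated.

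**Stronger readings that the documents do not support:**
- A reader might infer that AEs in included but untreated patients are necessarily excluded too. The protocol places AEs in the FAS, but SAP 8.4.2 and 8.4.3 say that all AEs collected in the eCRF are used, so the text is ambiguous.
- A reader might infer that the tables have nowhere to put an untreated patient. The randomised arm is known: SAP 8.4.3 and 8.4.4 tabulate by it, and SAP section 9 adds it to every listing. SAP section 5 does call for analysis as treated, but that inconsistency is a separate matter.
- A reader might infer that the DD rate is biased as the plan stands. The bias is conditional on such a patient existing. SAP 8.4.1 reports no loss to follow-up at data review, but does not say whether any included patient went untreated.

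**Conclusion.** The point holds as a conditional gap and is minor. As written, the protocol omits from DD incidence any deficiency that prevents all treatment of an included patient. Each such patient lowers the overall proportion by about 2 percentage points when other DDs are few, or about 4 points within an arm of 25. For one to three such patients and no other DD, the plan would show 0% where the all-included figure is 2% to 6%.

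These sizes rest on 50 included patients, assumed values of k and x, and nobody untreated for other reasons. With no untreated patient, the two summaries are identical. The primary endpoint and the ADE analyses are not affected. Scheduled DD collection at D0 comes after treatment (protocol 9.5.5.1 and Table 2), so for an untreated patient recording relies on the general rule in 9.13.3.

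**What to change.** - **SAP 8.4.2:** state that the DD row is summarised in all included, randomised patients, by randomised arm and overall, whether or not a session was delivered. Randomised arm is the safer grouping, because protocol 9.5.1 has device identity recorded per treatment session, and an undelivered session may have none.
- **SAP section 10:** list this as a change from protocol 9.6.3.2.
- **SAP 8.1:** add the reason for not being treated, with DD as a category. At present, reasons are tabulated only among treated patients and DD is not one of them.
- **Unchanged:** keep the FAS for ADEs, including the primary endpoint.

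The cost is a few sentences and table rows. DDs are already recorded from inclusion, and protocol 9.5.3.5 already has the reason for premature termination collected for each patient. Whether that form codes a DD as a reason is not shown and should be checked. The DD row will have a different denominator from the rest of its table and needs a footnote. Patients untreated for unrelated reasons will also enter it, which the new SAP 8.1 row makes visible. The DD rate may become slightly less favourable.
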